3.2 Rationale for Study Design

3.2.1 General Design Issues

The study is double-blind and placebo-controlled to avoid bias and facilitate interpretation of findings in the TRL345 dose group as compared to the placebo group. Safety review by the SMC after all subjects within a DG have completed Day 15 minimizes risks to subjects to be subsequently dosed at the next higher dose.

3.2.2 Selection of Population

The selection of healthy volunteers ensures the ability to obtain safety, PK data, and provide samples for an *ex vivo* assessments of the relationship of PK to antiviral activity (PD data) of TRL345.

3.3 Selection of Dose

Doses for this study are as follows:

- Dose level 1: 1 mg/kg
- Dose level 2: 10 mg/kg

Selection of this dose range is based on the following considerations:

Since the molecular weight of TRL345 is greater than 100,000 Dalton's and the drug is administered intravenously, interspecies comparisons of doses can be made on a mg/kg basis, rather than on the basis of doses normalized for total body surface area (See the FDA Guidance for Industry: Estimating the Maximum Safe Starting Dose in Initial Clinical Trials for Therapeutics in Adult Healthy Volunteers, July 2005).

The NOAEL was 150 mg/kg in a GLP repeat-dose toxicity study in Sprague-Dawley rats, which were dosed IV up to 150 mg/kg twice weekly for 28-days. The maximum recommended starting dose in humans of 10 mg/kg (Low Dose) has a safety margin of ~15-fold compared to the NOAEL in the rat.

Figure 1 depicts the modeled exposure curve in the Sprague-Dawley rat dosed at 150 mg/kg IV twice weekly for 28-days and shows the predicted TRL345 PK curves in humans after a single IV dose at 1.0 and 10.0 mg/kg.

[figure not shown]

Figure 1: Comparative TRL345 Exposure in the Rat and Humans

3.4 Safety Monitoring

A Safety Monitoring Committee (SMC) will review safety, dose escalation and overall timelines. They will review SAEs ([Section 7.2.2](#)) and \geq Grade 3 AEs that are “Likely” ([Section 7.2.3](#)) to be related to TRL345. Any infusion-related adverse events will be reported to the SMC within 24 hours. All data will be reviewed in an unblinded fashion upon completion of each DG.

The Sponsor will be responsible for notifying all study sites and Regulatory Authorities of any study recommendations, as appropriate.

3.5 Dose Escalation Criteria

The SMC will review all available safety data after the last subject in a DG has completed Day 15. They will evaluate the AEs, vital signs, and available laboratory results in the context of the established Study Pausing Rules (see below).

If Study Pausing Criteria are not met, they will make one of the following recommendations:

- Escalate to the next higher dose as planned
- Expand the DG to obtain additional safety information based on possible trends in laboratory assessments or Grade 1 (Mild) adverse events

3.6 Study Pausing Criteria

Should any one of the following criteria occur, the Sponsor will stop study recruitment and will not administer IP to any subject until the SMC has reviewed all available study data:

- First occurrence of an AE with severity Grade 3 (Severe) or Grade 4 (Potentially Life-Threatening) considered to be at least likely related to TRL345
- 2 or more subjects with an AE of severity Grade 2 (Moderate) in the same body class considered to be at least likely related to TRL345 (among total number of subjects dosed)
- Any other toxicity which in the opinion of the SMC precludes further dosing.

Following review of safety data, the SMC will make a recommendation to continue the study as planned, to modify, or to terminate the study.

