A Safety Monitoring Committee (SMC) will review safety, dose escalation, and overall timelines. The SMC will review SAEs ([Section 7.2.2](#)) and \geq Grade 3 AEs that are “Likely” ([Section 7.2.3](#)) to be related to TRL345. Any infusion-related adverse event will be reported to the SMC within 24 hours. All data will be reviewed in an unblinded fashion upon completion of each DG.

Dose Escalation

The SMC will review all available safety data after the last subject in a DG has completed Day 15. They will evaluate the AEs, vital signs, and available laboratory results in the context of the established Study Pausing Rules (see below).

If Study Pausing Criteria are not met, the SMC will make one of the following recommendations:

- Escalate to the next higher dose as planned
- Expand the DG to obtain additional safety information based on possible trends in laboratory assessments or Grade 1 (Mild) adverse events

Study Pausing Rules

Should any one of the following criteria occur, the Sponsor will stop study recruitment and will not administer IP to any subject until the SMC has reviewed all available study data:

- First occurrence of an AE with severity Grade 3 (Severe) or Grade 4 (Potentially Life Threatening) considered to be at least likely related to TRL345
- 2 or more subjects with an AE of severity Grade 2 (Moderate) in the same body class considered to be at least likely related to TRL345 (among total number of subjects dosed)
- Any other toxicity which in the opinion of the SMC precludes further dosing.

Following review of safety data, the SMC will make a recommendation to continue the study as planned, to modify, or to terminate the study.

Criteria for Evaluation:

Safety:

- Incidence and severity of AEs (includes vital signs, ECGs, laboratory evaluations, and physical examination findings)
- Incidence of SAEs

PK: Serum concentrations of TRL345 will be determined by ELISA

Immunogenicity: Incidence of baseline and IP-emergent ADA (i.e., anti-TRL345 antibodies) in serum will determined by electrochemiluminescence assay

PD: Serum samples will be taken to explore the capacity of various concentrations of TRL345 to neutralize CMV in *ex vivo* assessments

Statistical Methods

Sample Size: No formal sample size calculations were performed. The numbers of subjects per DG are typical for Phase 1 studies in healthy adult volunteers.

Analyses:

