3 STUDY DESIGN

3.1 Overall Study Design

This is a Phase 1, first-in-human, double-blind, single ascending dose study to assess the safety, PK, and PD of TRL345 in approximately 16 healthy male and female volunteers. Subjects aged 18-65, inclusive, will be screened.

Subjects will be assigned to a DG and randomized to receive TRL345 or placebo. There will be two dose groups. Each DG will be composed of 8 healthy volunteers; of these 6 will be randomized to receive TRL345 and 2 will be randomized to placebo. Any subject who withdraws before completing the study but after receiving IP may be replaced at the discretion of the Sponsor and in consultation with the Investigator. Any replacement subject will be assigned to receive the same treatment as the subject he or she is replacing.

An established ELISA assay available in commercial laboratories to detect IgG antibodies against CMV will be used to determine serostatus of subjects.

Dosing of the first two subjects (one randomized to TRL345 and one randomized to placebo) in each DG will be done on the same day. Dosing of the other subjects will occur at least 72 hours after the first two subjects have been dosed and following review of the blinded safety data from the first two subjects in the DG by the PI and Sponsor. After all subjects within a DG have completed Day 15, a Safety Monitoring Committee (SMC) will review all available safety data through Day 15 prior to making a recommendation regarding escalation to the next higher DG.

Subjects will be admitted to a Phase 1 research unit prior to the IV administration of a single dose of IP. In order to maintain the blind, subjects will be dosed as follows: DG1 will receive 1 mg/kg of TRL345 or 0.1mL/kg of placebo and DG2 will receive 10 mg/kg of TRL345 or 1mL/kg of placebo. All subjects (randomized to either TRL345 or placebo) will receive IP infused over 60 minutes.

Subjects will be closely monitored for AEs and SAEs, including infusion reactions (IRs), from onset of the infusion through discharge from the Phase 1 research unit. Subjects will be assessed for safety and tolerability, including AEs and SAEs at each follow-up visit after discharge through Day 76. A physical exam, vital signs, and routine clinical lab tests (chemistry and hematology) will be done on Days 1, 2, 3, 8, 15, 29, and 43. An ECG will be done on Days 1 and 8.

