7.1 Reporting Responsibilities

All AEs, including SAEs, will be recorded in the eCRF from start of IP infusion through Study Day 76. It is the responsibility of the Investigator or Sub Investigator(s) to perform assessment of AEs and SAEs at each study visit. Data describing AEs, and SAEs, will be entered in the subject’s medical record and eCRF. SAEs will be reported to the Sponsor as described in [Section 7.6](#).

Subjects who experience AEs, whether serious or not serious, should receive appropriate treatment and medical supervision as clinically indicated. All AEs must be followed until resolution/stabilization or until a time that is mutually agreed upon between the Medical Monitor and the Investigator.

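### The pausing rules contain no seriousness criterion, so one likely-related SAE graded 1 or 2 does not oblige the Sponsor to hold dosing

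*Protocol*

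**What the plan says.** Protocol Section 3.6 lists three events that oblige the Sponsor to suspend enrolment and withhold product until the SMC has looked at the data:

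- Criterion 1: "First occurrence of an AE with severity Grade 3 (Severe) or Grade 4 (Potentially Life-Threatening) considered to be at least likely related to TRL345".
- Criterion 2: "2 or more subjects with an AE of severity Grade 2 (Moderate) in the same body class", again judged at least likely related.
- Criterion 3: "Any other toxicity which in the opinion of the SMC precludes further dosing".

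The Synopsis, under Study Pausing Rules, repeats the list; its first item opens "First occurrence of an AE with severity Grade 3 (Severe) or Grade 4 (Potentially Life Threatening".

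Seriousness and severity are defined apart. Section 7.2.2 defines an SAE by outcome, or by medical judgement for important medical events. Section 7.2.4 assigns grades from an external FDA toxicity scale, given as a link.

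Other safeguards:

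- Section 3.4 puts SAEs before the SMC, requires infusion-related events to reach it within 24 hours, and provides an unblinded review when each dose group (DG) is complete.
- Section 7.6 gives sites 1 business day to report an SAE to the Sponsor. Marking an event as serious in the eCRF alerts the Medical Monitor or a designee.
- Section 4.3.4 names serious or unacceptable risk among conditions that could lead to a halt.
- Section 3.1 staggers dosing: "Dosing of the other subjects will occur at least 72 hours after the first two subjects have been dosed". Before the dose is raised, the SMC "will review all available safety data through Day 15 prior to making a recommendation regarding escalation to the next higher DG".

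**The concern.** Seriousness and grade measure different things. An event can be serious because of its outcome, or because a physician judges it medically important, without reaching Grade 3. Section 3.4 treats SAEs as a class of their own alongside likely-related events of Grade 3 or higher, but only the second class appears in the pausing rules.

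What is at stake is who decides, and when. For events inside criteria 1 and 2, dosing stops first and the SMC deliberates afterwards. For a single low-grade likely-related SAE the order is reversed: dosing may go on until the SMC or the Sponsor chooses to stop it. Outside infusion-related events, the protocol sets no time by which an SAE must reach the SMC. In a study with no earlier human exposure to the product, holding first is the more cautious order.

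**Working it through.** The plan states no operating characteristic for the pausing rules, so there is no figure to reproduce. The check applies the rules to one likely-related SAE at each grade, then bounds the dosing affected.

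**1. One likely-related SAE against Section 3.6 (the Synopsis gives the same result)**

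| Grade | Criterion 1 | Criterion 2 | Criterion 3 | Automatic hold? |
|---|---|---|---|---|
| 1 | not met | not met | only if the SMC so judges | no |
| 2 | not met | not met: one subject, two needed | only if the SMC so judges | no |
| 3 or 4 | met | not needed | not needed | yes |

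A Grade 2 SAE would count towards criterion 2 if a second subject had a likely-related Grade 2 event in the same body class.

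**2. Does anything else force a hold?**

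- Section 3.4: SMC review of SAEs, with no hold attached.
- Section 7.6: reporting and notification, with no hold attached.
- Section 4.3.4: a halt may be considered; it is not required.
- SAP: no pausing rule.

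**3. Could an SAE be graded 1 or 2?** Sections 7.2.2 and 7.2.4 set no minimum grade for an SAE. Section 7.5 likewise makes spontaneous abortion an SAE without naming a grade. How often this would happen depends on the linked scale, so no frequency can be given.

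**4. Upper bounds on dosing that no automatic rule would stop**

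Inputs from Section 3.1: 8 subjects per DG (6 TRL345, 2 placebo). The leading pair is one of each: "Dosing of the first two subjects (one randomized to TRL345 and one randomized to placebo) in each DG".

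- *Within a DG, after the 72-hour step:* 8 − 2 = 6 subjects, made up of 6 − 1 = 5 on TRL345 and 2 − 1 = 1 on placebo. This requires the SAE to occur in one of the leading pair, to arise after the 72-hour review or be passed by it, and to precede every other dose in that group. If it occurs in one of the other six, at most 6 − 1 = 5 subjects remain.
- *DG1 event after the escalation review:* up to all 8 DG2 subjects, 6 of them on TRL345. Such an event can be captured, since "All AEs, including SAEs, will be recorded in the eCRF from start of IP infusion through Study Day 76". The bound requires it to occur before the first DG2 dose, with neither the SMC nor the Sponsor acting.

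Both are extremes, not expected numbers.

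**The case against.** The strongest reply is that leaving low-grade SAEs to expert judgement is a legitimate design choice, and that the class may be almost empty. Every likely-related Grade 3 or 4 SAE already stops dosing. Section 3.4 sends SAEs to the SMC with no minimum grade, and ticking the serious box alerts the Medical Monitor whatever the grade. Once the SMC invokes criterion 3, the hold is binding. A careful Sponsor might well stop anyway.

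Much of this stands, and it limits the size of the point. It does not close the gap, because none of these steps makes the Sponsor hold dosing while the SMC considers the event.

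Four stronger readings should be resisted:

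- A reader might infer that SAEs do not pause the study. Those that are likely related and Grade 3 or 4 do.
- A reader might infer that a DG1 SAE after Day 15 escapes scheduled review. Section 3.4 also has an unblinded review when each DG is complete. Completion is not defined, so its timing relative to DG2 dosing is unclear, but the absence of any later review is not established.
- A reader might infer that all follow-up after Day 15 is unprotected. A pause protects only people not yet dosed; after the last DG2 infusion there is no planned dose left to withhold.
- A reader might infer that Section 3.5 confines the SMC to escalating or expanding. Those options apply when no pausing criterion is met. An SMC that thinks dosing unsafe can invoke criterion 3, and Section 3.6 then lets it recommend modification or termination.

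**Conclusion.** The point holds in a narrow form. One event class is affected: a single likely-related SAE graded 1 or 2. For that class a hold depends on SMC opinion under criterion 3, or on the discretionary halt in Section 4.3.4.

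The conclusion rests on the protocol's wording and on one assumption: that the linked scale allows a serious event to be graded below 3. Nothing in either document rules that out, and nothing shows how common it would be. Confidence is medium for that reason. The change is worth making because it is cheap and the study is first-in-human, not because a frequent failure has been shown.

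Reporting time is a secondary matter. A likely-related Grade 3 event that is neither serious nor infusion-related does meet criterion 1, but the protocol sets no numeric limit for telling the Sponsor; Section 9.6 asks only for timely eCRF submission. This is separate from the missing criterion and does not add to its weight.

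**What to change.** Add one bullet to Section 3.6 and to the Synopsis: *any SAE (including death) considered likely related to TRL345, regardless of grade*. Death is named for clarity only.

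Add one sentence to Section 7.6: events meeting this bullet or criterion 1 are reported to the Sponsor and the SMC within 24 hours of site awareness. Section 3.4 already assigns both classes to the SMC, and 24 hours is the limit it already sets for infusion-related events. The limit need not extend to Grade 2 events generally or to criterion 3.

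The cost is small: a possible short pause for an SAE later judged unimportant, and slightly faster reporting of a few events. The change does alter a stated stopping rule, so it needs a protocol amendment. Sample size and planned analyses are unaffected.

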3.7 Subject Participation and Study Duration

The total duration of enrollment is estimated to be 4 months. The duration of each subject's participation (including Screening) is approximately 12 weeks. Thus, the study is expected to last approximately 7 months.

4 SUBJECT POPULATION

Approximately 16 subjects who meet the eligibility criteria will be enrolled.

4.1 Inclusion Criteria

1. Healthy male and non-pregnant, non-breast-feeding female subjects at between 18 and 65 years of age, inclusive, and representative of the general population
2. Willing and able to provide written informed consent.
3. Availability for the entire duration of the study, and willingness to adhere to protocol requirements
4. In good health, as determined by lack of clinically significant abnormalities in health assessments performed at the Screening Visit, as judged by the Principal Investigator (PI) or as delegated by the PI to a physician or nurse practitioner as sub-investigator.
5. Men and women of child bearing potential (WOCBP) must be willing to practice a highly effective method of contraception that may include, but is not limited to, abstinence, sex only with persons of the same sex, monogamous relationship with vasectomized partner, vasectomy, hysterectomy, bilateral tubal ligation, licensed hormonal methods, or intrauterine device (IUD) for 28 days before Screening and through Day 76. Men must also refrain from donating sperm from Day 1 through Day 76.

4.2 Exclusion Criteria

1. Inability to tolerate blood draws or has poor venous access
2. Body mass index (BMI) <18.5 or ≥ 35 kg/m²
3. Clinically significant vital sign abnormalities (systolic blood pressure lower than 90 or over 160 mmHg; diastolic blood pressure lower than 50 or over 100 mmHg; or, heart rate less than 45 or over 100 bpm) at the Screening Visit
4. ECG with clinically significant findings, including:
 - a. Conduction disturbance (complete left or complete right bundle branch block or nonspecific intraventricular conduction disturbance with QRS ≥ 120 msec, PR interval ≥ 220 msec, any second- or third-degree atrioventricular block, or prolongation of the QT interval corrected according to Fridericia's correction [>450 msec male and >460 msec female])
 - b. Significant repolarization (ST-segment or T-wave) abnormality; or
 - c. Significant atrial or ventricular arrhythmia; or
 - d. Frequent atrial or ventricular ectopy (e.g., frequent premature atrial contractions, 2 premature ventricular contractions in a row); or
 - e. ST-elevation consistent with ischemia or evidence of past or evolving myocardial infarction.
5. Presence of any gastrointestinal pathology (e.g., chronic diarrhea, inflammatory bowel diseases), unresolved gastrointestinal symptoms (e.g., diarrhea, vomiting), or progressive liver or kidney disease

6. Diagnosis of diabetes mellitus
7. History of acute or chronic pancreatitis or upper right quadrant postprandial discomfort or pain within the last 2 years
8. Clinically relevant medical conditions that, in the opinion of the PI, may interfere with the evaluation of the trial drug, e.g., progressive cardiovascular disease
9. Concurrent acute or chronic infections (e.g., viral infections, except chronic recurrent herpes simplex infections)
10. Significant abnormal safety labs, defined as:
 - Greater than 30% outside of the normal range for any of the following: hemoglobin, white blood cell (WBC) count, platelet count, neutrophil count and blood urea nitrogen
 - Aspartate aminotransferase (AST), alanine aminotransferase (ALT), alkaline phosphatase (ALP), direct bilirubin or indirect bilirubin $>2 \times$ the upper limit of normal
 - Activated partial thromboplastin time (aPTT) prolongation $>1.5 \times$ ULN
 - Hemoglobin A1C (HbA1C) $>5.6\%$
 - Fasting glucose level of ≥ 100 mg/dl (5.6 mmol/L)
 - Renal function based on the, i.e., estimated creatinine clearance < 70 mL/min (Cockcroft-Gault formula using ideal body weight)
 - Hemoglobin ≤ 128 g/L (males) and ≤ 115 g/L (females), and hematocrit $\leq 37\%$ (males) and $\leq 32.0\%$ for females
11. Positive test results for HIV, Hepatitis B (HBsAg), or Hepatitis C (HCV) at the Screening Visit
12. History of significant drug abuse within one year prior to the Screening Visit and/or ongoing
13. History of significant alcohol abuse within one year prior to the Screening Visit defined as more than fourteen units of alcohol per week [one “unit” is equal to approximately $\frac{1}{2}$ pint [200 mL] of beer, 1 small glass [100 mL] of wine, or 1 measure [25 mL] of spirits)
14. Positive test for drugs of abuse, ETOH and nicotine (cotinine) at the Screening Visit
15. Positive serum beta-human chorionic gonadotropin test for pregnancy, pregnant, or nursing women
16. Unwilling to refrain from donating blood or plasma during the study.
17. Use of any new prescription medication or over-the-counter (OTC) product (including natural food supplements, vitamins, herbs) within 14 days prior to dosing
18. Receipt of any vaccine or booster within 14 days prior to Day 1 or planned vaccination or booster within 4 weeks after IP administration
19. Any planned medical intervention or personal event that might interfere with the ability to comply with the study requirements
20. Is current study site staff paid entirely or partially by the contract for this trial, or staff who are supervised by the PI or sub-PI

21. Receipt of an investigational product, or participation in another trial involving a marketed or investigational drug within 30 days of Day 1, or 5 half-lives of the investigational drug, whichever is longer
22. Any other comorbidity or condition that, in the opinion of the Investigator would make the subject unsuitable for the study or unable to comply with the study requirements

4.3 Subject and Study Discontinuation

4.3.1 Screening Failures

Subjects who sign and date the informed consent form (ICF) but who fail to meet the inclusion and exclusion criteria are defined as screen failures. A screening log, which documents the subject's initials and reason(s) for screen failure, is to be maintained for all screen failures. A copy of the log should be retained in the Investigator's study files.

A subject who has failed screening may be rescreened at the discretion of the Investigator and Sponsor. In these cases, a new screening number must be assigned for each subject who is rescreened, and a new informed consent form must be signed.

4.3.2 Premature Discontinuation from Study

A subject may be prematurely discontinued from the study for any of the following reasons:

- Subject wishes to withdraw consent for reasons other than an AE
- Subject is lost to follow-up
- Subject non-compliance or unwillingness to comply with the procedures required by the protocol
- Investigator discretion
- Sponsor request

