2 OBJECTIVES AND ENDPOINTS

2.1 Objectives

2.1.1 *Primary Objective*

- Assess the safety and tolerability of TRL345 when administered intravenously (IV) as a single dose in healthy adult volunteers

2.1.2 *Secondary Objectives*

The secondary objectives are to:

- Characterize the pharmacokinetics (PK) of a single IV infusion of TRL345 overall and by DG
- Assess the immunogenicity of TRL345 as measured by anti-drug antibodies (ADAs)

2.1.3 *Exploratory Objective*

The exploratory objectives are to:

- Explore the pharmacodynamics (PD) of TRL345 in an *ex vivo* study using serum samples to explore the capacity of various concentrations of TRL345 to neutralize HCMV in human serum
- Explore if there are any differences in adverse events, clinical labs, or PK across dose groups to explore if there are any signs of off-target binding of TRL345

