8.5 Safety Analyses

8.5.1 Adverse Events

All AEs, including IRs, and SAEs, will be coded using the Medical Dictionary for Regulatory Affairs (MedDRA). Frequency tables will be presented by dose and treatment group for all AEs and SAEs by System Organ Class (SOC) and Preferred Term (PT). Frequency tables will also be produced by dose and treatment group for AEs leading to discontinuation from IP and study, by maximum severity, and by causality. No formal statistical testing will be done.

AEs and SAEs will be summarized overall, by severity, and relatedness, and may also be summarized within specific time intervals (e.g., within 4 hours of infusion).

Clinically significant physical exam and lab abnormalities will be reported as AEs and summarized as described above.

8.5.2 *Laboratory Evaluations and Vital Signs*

Quantitative data (e.g., clinical lab results) will be summarized by presenting mean, median, SD, and range by dose and treatment group. Laboratory abnormalities will be analyzed as safety outcomes by summarizing frequency, severity, and changes from baseline. Other analyses may include but are not limited to the following: examination of shift tables and pre-established severity grades. Additional serum samples will be taken and stored for possible exploratory analyses that may be necessary to further explore any unexpected safety or tolerability observations.

8.5.3 *Concomitant Medications*

Concomitant medications will be coded using the most current World Health Organization (WHO) drug dictionary and summarized by drug class and medication term, with results presented by dose and treatment group.

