## **8.1 Subject Disposition**

Subjects will be summarized by the number and percent of subjects dosed, completed the study, and discontinued the study (with discontinuation reasons) by treatment (pooled placebo, active treatment, active treatment total) and overall.

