## **9. SUMMARY OF CHANGES FROM PROTOCOL-PLANNED ANALYSIS**

The protocol states that the following safety data will be summarized: physical examinations, medical history, disease history, concomitant medications, SAEs, AEs leading to discontinuation from study, AEs leading to discontinuation of study product, AEs within a specified time interval from dosing, and lab abnormalities (by severity). However, these analyses will not be performed and are not included in this SAP.

The protocol states that the all subjects receiving TRL345 will be included in the analyses. However, the Pharmacokinetic Population and the Pharmacokinetic Analysis Population were defined in this SAP for the PK analyses.

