Appendix 16.2.1.1 Subject Disposition (Safety Population)

Dose Group	Subject Number	Randomized /Actual Treatment	End of Treatment				End of Study			
			Did Subject Prematurely Discontinue?	Treatment Discontinuation Date	Primary Treatment Discontinuation Reason	Specify	Did Subject Complete the Study?	Date of Completion or Discontinuation	Primary Study Discontinuation Reason	Specify
1	0001	A/A	No				Yes	DDMMYYYY		
	0002	P/P	No				No	DDMMYYYY	Personal Reason	XXXXXXXX
	0003	A/A	Yes	DDMMYYYY	Adverse Event	XXXXXXX	No	DDMMYYYY	Other	XXXXXXXX

Programmer Note: Subject numbers will be presented as contained in clinical database (i.e. 0001, etc.)

Treatment A: A single 1-hour intravenous infusion of 1 mg/kg TRL345 (Dose Group 1)  
 Treatment B: A single 1-hour intravenous infusion of 10 mg/kg TRL345 (Dose Group 2)  
 Treatment P: A single 1-hour intravenous infusion of matching placebo (Dose Groups 1 and 2)

Source: SDTM.< >; ADaM.< >  
 Program: /CAXXXXX/sas\_prg/stsas/lis/programname2022Q1.sas DDMMYYYY HH:MM

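### The protocol's withdrawal reasons omit adverse events and the SAP drops both AE-discontinuation tables, so AE-driven infusion stops reach only listings and AE-driven study withdrawals may carry another label

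*Protocol*

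**What the plan says.** - **Objective.** Protocol 2.1.1: "Assess the safety and tolerability of TRL345 when administered intravenously (IV) as a single dose in healthy adult volunteers".
- **Reasons for leaving the study.** Protocol 4.3.2 has five entries. One is "Subject wishes to withdraw consent for reasons other than an AE". The other four are loss to follow-up, non-compliance, investigator discretion and sponsor request.
- **Planned tables.** Protocol 8.5.1: "Frequency tables will also be produced by dose and treatment group for AEs leading to discontinuation from IP and study".
- **Cancelled tables.** SAP 9 names, among the analyses that the protocol promised, "AEs leading to discontinuation from study, AEs leading to discontinuation of study product". It then states: "However, these analyses will not be performed and are not included in this SAP". No rationale follows.
- **What the SAP keeps.** SAP 8.1 counts subjects who "discontinued the study (with discontinuation reasons"), by treatment and overall. Shells IDS and CDS carry this as a study-discontinuation row with open reason rows beneath it. Listing 16.2.1.1 has a treatment-discontinuation reason and, separately, a field headed "Primary Study Discontinuation Reason". SAP 8.4 and listing 16.2.7.1 show the action taken for each AE, subject by subject.

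**The concern.** The consent entry in 4.3.2 deliberately sets AE-driven withdrawal aside, and no other entry then receives it. A site working from that list has only a non-specific label for a subject who leaves because of an AE. The protocol's own safeguard was the pair of tables in 8.5.1, which report discontinuation from the AE side and do not depend on the disposition label. SAP 9 removes that safeguard.

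At stake is whether the report's summary tables show how many subjects stopped because they did not tolerate the product. In a first-in-human trial with tolerability in the primary objective, a reader looks for that count. Protocol 4.3.3 also allows a subject who withdraws after dosing to be replaced, which makes a clear record of why the subject left more useful.

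**Working it through.** The plan states no figure to reproduce: Protocol 8.1 reports no formal sample size calculation, and the analysis is descriptive. The check is to trace two events through the planned outputs.

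**Can the events occur?** Yes. IP is a single 60-minute infusion, so discontinuation of IP means a stopped infusion, and Protocol 5.7 foresees this for a severe infusion reaction. Withdrawal from the study can happen at any time up to Day 76.

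| Output | Infusion stopped for an AE | Study withdrawal for an AE |
|---|---|---|
| Disposition tables IDS and CDS (SAP 8.1) | No row: the rows are dosed, completed, discontinued from study, and reason | Counted, under whatever reason the form records |
| TEAE tables 14.3.1.1 to 14.3.1.3 | The AE is counted; that it stopped the infusion is not shown | The AE is counted; that it led to withdrawal is not shown |
| Protocol 8.5.1 tables of AEs leading to discontinuation | Cancelled by SAP 9 | Cancelled by SAP 9 |
| Listing 16.2.1.1 | Treatment-discontinuation reason on the subject's row | Study-discontinuation reason on the subject's row |
| Listing 16.2.7.1 | Action taken and infusion-reaction flag | AE, grade, relationship and action on study product |

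**Reading the left column.** No summary table identifies the event. This holds whatever the case report form contains, because the shells have no place for it. SAP 9 also drops the summary of AEs within a set interval from dosing, so that indirect route is closed too.

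**Reading the right column.** The subject is counted. Whether the reason row says adverse event depends on the form's code list, which the documents do not give. The sample reasons in listing 16.2.1.1 (a personal reason, and other) are not among the five in 4.3.2. The protocol list and the SAP's illustration therefore do not match, and nothing says which governs.

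**Linkage.** The TEAE tables give counts by System Organ Class and Preferred Term, and by severity and relationship. None has a column for action or discontinuation.

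**Size of one event.** Each dose group has 6 active subjects (Protocol 3.1), so there are 2 × 6 = 12 active subjects in all.
- Within a dose group: 1/6 = 16.7%, shown as 17% under the SAP's integer rule for percentages.
- Across active subjects: 1/12 = 8.3%, shown as 8%.

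**The case against.** The strongest reply has four parts.

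1. **Every study withdrawal is already summarized.** SAP 8.1 counts each one with a reason, and the AE itself is in the TEAE tables. This stands. A reader might infer that withdrawals for intolerance vanish from every summary, or that the disposition table would show 0% for AE. The documents support neither: the subject is counted, and only the label is uncertain.

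2. **Protocol 4.3.2 is not a code list.** It is permissive text, and no sentence in either document says that the disposition reasons are taken from it. The form may already offer an adverse-event reason. This also stands, and it rules out saying that sites must use another label. A reader might point to sample subject 0003 in listing 16.2.1.1, whose treatment stopped for an adverse event while the study reason reads other. That row proves nothing: SAP 11.4 says the shells may not reflect every aspect of the study, and the values are placeholders.

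3. **The listings are short.** With 16 planned subjects, a reader can find a stopped infusion on the subject's own row of listing 16.2.1.1. That is true and limits the harm. It does not turn a listing into a summary by treatment, and a small trial also makes the missing table very easy to produce.

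4. **The omission is declared, and discontinuation is not a named safety endpoint.** Both are correct. SAP 9 is the proper place for such a change, and Protocol 2.2.1 names incidence and severity of AEs and other findings. But tolerability is in the objective, the protocol promised these tables in its safety analyses, and declaring a change is not the same as justifying it.

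**Conclusion.** The point holds in this form. Protocol 4.3.2 excludes AE-driven withdrawal from its consent reason and supplies no adverse-event reason. SAP 9 cancels, without explanation, both planned tables of AEs leading to discontinuation. Three consequences follow.

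- An infusion stopped for an AE is identified in no summary table, only in listings. This rests on the SAP text and shells alone.
- A study withdrawal for an AE is counted, but possibly under a non-specific label. This is conditional on the form's code list, which cannot be checked here.
- No table connects a TEAE to discontinuation of IP or from the study. This also rests on the SAP alone.

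A single event is 17% of an active dose group or 8% of all active subjects. These fractions show how much one subject weighs; they do not predict that an event will occur. The matter should be corrected, but it concerns coding and reporting only. It does not call into question collection of the AEs or any clinical rule for stopping an infusion.

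**What to change.** 1. **Protocol 4.3.2:** add an adverse-event reason, and state that consent withdrawn because of an AE is recorded there. Check that the case report form list behind the reason rows of IDS and CDS has the same entry, and make the two lists agree.
2. **SAP 9:** remove the two discontinuation items from the list of analyses not performed.
3. **SAP 8.4 and the shells:** add one table by P, A, B and Active Total, giving the number and percentage of subjects with a TEAE leading to discontinuation of IP, and with a TEAE leading to discontinuation from the study. A lighter alternative is a block of treatment discontinuation by reason in IDS and CDS. That covers stopped infusions but does not by itself name the AE.

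The cost is a line of protocol text, a code-list check and one short table. The AE action field and the two discontinuation-reason fields already appear in the listing shells, so no new assessment is needed. If the form lacks an adverse-event reason for leaving the study, one value must be added to its list.
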